### **6.3 Laboratory Test Result Abnormalities**

The following laboratory test result abnormalities should be captured on the nonserious AE CRF page or SAE Report Form (paper or electronic) as appropriate:

Any laboratory test result that is clinically significant or meets the definition of an SAE

Any laboratory test result abnormality that required the subject to have study drug discontinued or interrupted

Any laboratory test result abnormality that required the subject to receive specific corrective therapy

It is expected that, wherever possible, the clinical rather than laboratory term would be used by the reporting Investigator (eg, anemia vs low hemoglobin value).

### **6.4 Pregnancy**

If, following initiation of the investigational product, it is subsequently discovered that a study subject is pregnant or may have been pregnant at the time of investigational product exposure, including during at least 5 half-lives plus 30 days after product administration, the Investigator must immediately notify the BMS Medical Monitor/Designee of this event and complete and forward a Pregnancy Surveillance Form to BMS Designee within 24 hours and in accordance with SAE reporting procedures described in [Section 6.1.1](#).

In most cases, the study drug will be permanently discontinued in an appropriate manner (eg, dose tapering if necessary for subject safety). If the Investigator determines a possible favorable benefit-risk ratio that warrants continuation of study treatment or reinitiation of study treatment, a discussion between the Investigator and the BMS Medical Monitor/designee must occur. If, for whatever reason, pregnancy has ended, confirmed by negative serum pregnancy test, treatment may be resumed (at least 3 weeks and not greater than 6 weeks after the pregnancy has ended), following approvals of participant/Sponsor/IRB/IEC, as applicable.

Protocol-required procedures for study discontinuation and follow-up must be performed on the subject unless contraindicated by pregnancy (eg, x-ray studies). Other appropriate pregnancy follow-up procedures should be considered if indicated.

The Investigator must immediately notify the BMS (or designee) Medical Monitor of this event and complete and forward a Pregnancy Surveillance Form to BMS (or designee) within 24 hours and in accordance with SAE reporting procedures described in [Section 6.1.1](#).

Follow-up information regarding the course of the pregnancy, including perinatal and neonatal outcome and, where applicable, offspring information, must be reported on the Pregnancy Surveillance Form.

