### **3.5 Discontinuation of Subjects From Treatment**

Subjects MUST discontinue investigational product (and noninvestigational product at the discretion of the Investigator) for any of the following reasons:

Subject's request to stop study treatment

Pregnancy

Termination of the study by BMS

Loss of ability to freely provide consent through imprisonment or involuntarily incarceration for treatment of either a psychiatric or physical (eg, infectious disease) illness

Inability to comply with protocol requirements

- Progressive disease (see also [Section 4.3.4](#) for details regarding continuing treatment beyond initial assessment of PD per RECIST)

Clinical deterioration as assessed by the Investigator

Adverse event meeting discontinuation criteria ([Section 4.3.5](#))

All subjects who discontinue investigational product should comply with protocol-specified follow-up procedures as outlined in [Section 5](#). The only exception to this requirement is when a subject withdraws consent for all study procedures, including post-treatment study follow-up, or loses the ability to consent freely (ie, is imprisoned or involuntarily incarcerated for the treatment of either a psychiatric or physical illness).

If study treatment is discontinued prior to the subject's completion of the study, the reason for the discontinuation must be documented in the subject's medical records and entered on the appropriate case report form (CRF) page.

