#### **4.3.5 Guidelines for Permanent Discontinuation**

Subjects meeting any of the following criteria will be required to permanently discontinue all study drug(s) (BMS-986016 in Part A and Part A1; BMS-986016 and nivolumab [BMS-936558] or BMS-986213 in Parts B, C, D, and E):

Any  $\geq$  Grade 2 drug-related uveitis, eye pain, or blurred vision that does not respond to topical therapy and does not improve to Grade 1 severity within the retreatment period OR requires systemic treatment

Any  $\geq$  Grade 3 nonskin, drug-related AE lasting  $> 7$  days or recurs, with the following exceptions for laboratory abnormalities, drug-related uveitis, pneumonitis, bronchospasm, hypersensitivity reactions, infusion reactions, and endocrinopathies

Any  $\geq$  Grade 3 drug-related myocarditis, uveitis, pneumonitis, bronchospasm, or hypersensitivity reaction of any duration requires discontinuation.

Any  $\geq$  Grade 3 infusion reaction that does not return to Grade 1 in 6 hours or less requires discontinuation.

Any  $\geq$  Grade 3 drug-related endocrinopathies adequately controlled with only physiologic HRT do not require discontinuation.

Any  $\geq$  Grade 3 drug-related laboratory abnormalities do not require treatment discontinuation except:

- Any  $\geq$  Grade 3 drug-related thrombocytopenia  $> 7$  days or associated with bleeding requires discontinuation.
- AST, ALT, or bilirubin abnormalities that meet DLT criteria ([Section 3.1.2.6](#)) (In most cases of AST or ALT elevation meeting DLT criteria, study drugs will be permanently discontinued. If the Investigator determines a possible favorable benefit-risk ratio that warrants continuation of study drugs, a discussion between the Investigator and the BMS Medical Monitor/designee must occur.)
- Elevated troponin that meets DLT criteria ([Section 3.1.2.6](#))

Any Grade 4 drug-related AE or laboratory abnormality (including, but not limited to, creatinine, AST, ALT, or total bilirubin), except for the following events, which do **not** require discontinuation:

- Grade 4 neutropenia  $\leq$  7 days
- Grade 4 lymphopenia or leukopenia
- Isolated Grade 4 amylase or lipase abnormalities that are not associated with symptoms or clinical manifestations of pancreatitis
- Isolated Grade 4 electrolyte imbalances/abnormalities that are not associated with clinical sequelae and are corrected with supplementation/appropriate management within 72 hours of their onset

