**Table 5.1-2: On-treatment Procedural Outline for Q2W and Q4W BMS-986016/Nivolumab Treatment Regimens Parts A Through E**

Procedure	Treatment Cycles					Notes
	Day 1	Day 15	Day 29	Day 43	Day 50-56 a	
Visit Window for Q2W	± 2 days	± 2 days	± 2 days	± 2 days		
Visit Window for Q4W	± 3 days	± 3 days	± 3 days	± 3 days		
	See Notes		See Notes			Serum or urine pregnancy test may be performed (urine pregnancy test: minimum sensitivity 25 IU/L or equivalent units of hCG). If results are positive, hold all study drug and perform confirmatory testing. If pregnancy is confirmed, permanently discontinue all study drug and immediately notify Sponsor per Section 6.4 .
Assess adequate contraceptive use	X See Notes		X See Notes			For WOCBP: Assess for continued use of acceptable methods of contraception; see Appendix 1 . As of Protocol Amendment 14 , no contraception requirements for relatlimab and nivolumab are necessary for male participants.
Adverse Event and ConMed Assessment						
Monitor for nonserious adverse events	X	X	X	X		
Monitor for serious adverse events	X	X	X	X		
ConMed assessment	X	X	X	X		
Sample Collection						
Pharmacokinetic (PK) assessments	See Section 5.5 and Table 5.5.1-1 and Table 5.5.1-2 for Q2W dosing See Table 5.5.1-3 for Q4W dosing Part B and Part C (Bladder Cohort), Table 5.5.1-4/Table 5.5.1-5 for Part D and Part E				Performed in all subjects	

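### Section 6.4 leaves open continuing study drug in a confirmed, ongoing pregnancy, while Section 3.5 and Table 5.1-2 require stopping; no text says which rule governs

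*Combined protocol and SAP*

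**What the plan says.** Three places in the protocol deal with study drug when a participant is pregnant.

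- **Section 3.5 (Discontinuation of Subjects From Treatment)** opens its list with "Subjects MUST discontinue investigational product (and noninvestigational product at the discretion of the Investigator) for any of the following reasons". Pregnancy is on the list with no qualifier.
- **Table 5.1-2 (on-treatment schedule), pregnancy test row**, holds all drug on a positive test while confirmation is sought. It then states: "If pregnancy is confirmed, permanently discontinue all study drug and immediately notify Sponsor", with a pointer to Section 6.4.
- **Section 6.4 (Pregnancy)** is triggered when it is found that "a study subject is pregnant or may have been pregnant at the time of investigational product exposure". Its default is "In most cases, the study drug will be permanently discontinued in an appropriate manner". The next sentence covers continuing or reinitiating treatment. Its premise is "If the Investigator determines a possible favorable benefit-risk ratio that warrants continuation of study treatment", and its condition is that "a discussion between the Investigator and the BMS Medical Monitor/designee must occur". A separate sentence then allows treatment to resume once a pregnancy has ended. The conditions are a negative serum test, an interval of at least 3 and at most 6 weeks, and resumption "following approvals of participant/Sponsor/IRB/IEC, as applicable".

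**The concern.** Whether an investigational antibody combination may be given during a known pregnancy should have one answer. An investigator who wants to keep treating a woman with a confirmed pregnancy finds two texts that say stop and a third that provides for carrying on after a conversation.

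The safeguards also run the wrong way. Restarting after the pregnancy is over needs named approvals. Continuing while it is ongoing, when there is a fetus to expose, names none.

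The stake is participant and fetal safety and consistent conduct across sites. It is not a matter of inference: no estimate, error rate or sample size depends on it.

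**Working it through.** No arithmetic applies. The check sets the three texts against the three situations that can arise.

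| Situation | Section 3.5 | Table 5.1-2 | Section 6.4 | Consistent? |
|---|---|---|---|---|
| Positive test, not yet confirmed | Pregnancy not yet established | Hold drug, confirm | Discussion with the Medical Monitor possible | Yes: drug is held while the case is discussed |
| Confirmed, ongoing | Must discontinue | Discontinue permanently | Discontinue in most cases; continuation contemplated after a discussion | No |
| Ended | Must discontinue, but not said to be permanent | Discontinue permanently | May resume on stated conditions | 3.5 yes; the table no |

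Five readings that might remove the conflict in the second row were tried.

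1. *Section 6.4 concerns only unconfirmed cases.* Its trigger covers a subject who is pregnant as well as one who may have been, and nothing narrows the continuation sentence.
2. *It concerns only ended pregnancies.* These have their own sentence and conditions, so continuation must refer to something else. The approvals belong to that later sentence and do not carry back.
3. *The table imports the Section 6.4 exception.* Its pointer attaches to notifying the Sponsor, not to the order to discontinue.
4. *Section 3.5 is shorthand for a rule with exceptions.* In the same list, progressive disease points to Section 4.3.4 and adverse events point to Section 4.3.5. Pregnancy points nowhere.
5. *The general reinitiation clause in Section 4.3.5 settles it.* That clause covers restarting after discontinuation in subjects who again meet eligibility, which includes the negative pregnancy test in inclusion criterion 3(d). It largely bars restarting in an ongoing pregnancy but does not address never having stopped.

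The missing approval is a real gap, because the protocol states approval where it wants it. Section 4.3.5 asks for Medical Monitor approval as well as discussion before treatment goes on after certain Grade 4 endocrinopathies. Section 4.3.3 asks for approval before resuming when a toxicity resolves more than 6 weeks after the last dose. A site also has some reason to treat the Section 6.4 wording as operative, since Section 4.3.5 uses the same formula as a working exception for AST/ALT elevations that meet DLT criteria: "warrants continuation of study drugs, a discussion between the Investigator and the BMS Medical Monitor/designee must occur".

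**The case against.** The strongest reply is that Section 6.4 never says treatment may continue. It requires a discussion if the Investigator thinks continuation is warranted. Where the section does grant permission, for an ended pregnancy, it says so and attaches conditions. On this view the only operative dosing rules for a confirmed pregnancy are Section 3.5 and Table 5.1-2, and a site can satisfy all three texts by stopping drug and discussing the case. Section 9.1.1 adds a backstop: a deviation needs prior IRB/IEC approval unless it removes an immediate hazard. The AST/ALT parallel is also imperfect, because that exception sits inside the discontinuation list it qualifies, whereas Section 6.4 sits among the adverse event provisions.

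Much of this stands. A reader might infer that Section 6.4 authorizes dosing in pregnancy. It does not: it requires a discussion and is silent on what follows. Nor could a site simply proceed unseen. Section 6.4 requires immediate notification and a form within 24 hours, and Section 6.1 has pregnancy handled as a serious adverse event.

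The reply does not close the gap, however. Section 9.1.1 governs departures from the protocol; it does not say whether acting on Section 6.4 is a departure or compliance. Notification tells the Sponsor about the case without settling whether the next dose may be given. A discussion about continuing would have little purpose if the answer were always no.

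**Conclusion.** The point holds as an internal inconsistency in a safety rule, with two parts. The main one is that the documents do not say which rule governs a confirmed, ongoing pregnancy. The lesser one is that *permanently* in Table 5.1-2 contradicts the resumption that Section 6.4 permits after a pregnancy has ended. Section 3.5 requires discontinuation without calling it permanent, so it does not share that second conflict.

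The practical reach is small. The documents give no count of pregnancies. Contraception is mandatory for women of childbearing potential, and enrollment closed on 30-Jul-2021 (Appendix 7). The women affected are those still on treatment, which may run past 5 years (Section 3.1), and those still eligible for rechallenge if they restart.

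A reader might try to infer from the pregnancy-test schedule how many doses a continued participant would receive before the next test. The documents support no such figure. If Table 5.1-2 is followed, no dose follows a confirmed positive result; any count assumes the table is ignored at one test and obeyed at the next.

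The conclusion rests on the wording alone and assumes no unpublished instruction to sites that sets precedence. It is worth correcting because the possible harm is serious and the correction is nearly free.

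**What to change.** - **Section 6.4:** state that study drug must not be continued or restarted during a confirmed, ongoing pregnancy. Limit the benefit-risk discussion with the Medical Monitor to unconfirmed or ended pregnancies. Keep resumption after an ended pregnancy as the sole exception, on the existing conditions (negative serum test, the 3-to-6-week interval, the stated approvals).
- **Section 3.5:** add to the pregnancy entry a cross-reference to that exception, as the progressive disease entry already has for its own.
- **Table 5.1-2:** qualify *permanently* with the same cross-reference.

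The cost is wording in three places, with no effect on data collection, sample size or analysis. Amendment 15 already edited Section 6.4, so a further amendment could carry the change.

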## **6.5 Overdose**

An overdose is defined as the accidental or intentional administration of any dose of a product that is considered both excessive and medically important. See [Section 6](#) for reporting of overdose.

## **6.6 Potential Drug-induced Liver Injury**

Wherever possible, timely confirmation of initial liver-related laboratory abnormalities should occur prior to the reporting of a potential DILI event. All occurrences of potential DILIs meeting the defined criteria must be reported as SAEs (see [Section 6.1.1](#) for reporting details).

Potential DILI is defined as:

1. Aminotransaminase (AT) (ALT or AST) elevation > 3 times ULN  
AND
2. Total bilirubin > 2 times ULN, without initial findings of cholestasis (elevated serum alkaline phosphatase),  
AND
3. No other immediately apparent possible causes of AT elevation and hyperbilirubinemia, including, but not limited to, tumor progression; acute viral hepatitis; cholestasis; preexisting hepatic disease; or the administration of other drug(s), herbal medications, and substances known to be hepatotoxic.

**Given the organ-specific nature of HCC, the definition of potential DILI is defined differently specifically for HCC subjects.** The rationale for HCC-specific DILI language as follows: 1) standardization of the DILI definition so that a unified approach is taken across the BMS HCC program; 2) concern that the previous language may not be sensitive to capture all potential cases given the lack of a requirement for a concomitant elevation in transaminases and bilirubin and the significant increase in total bilirubin regardless of baseline value; and 3) alignment with the daclatasvir direct-acting antiviral agent (DAA) program, which has criteria that have been developed after consultation with Health Authorities for subjects with chronic HCV infection with underlying liver disease and therefore consistent with the patient population in this study.

Therefore, potential DILI for HCC subjects is defined as:

1. AT (ALT or AST) elevation > 10 times ULN  
AND
2. Total bilirubin > 2 times ULN or baseline value (if elevated bilirubin at study entry)

AND

3. No other immediately apparent possible causes of AT elevation and hyperbilirubinemia, including, but not limited to, tumor progression; acute viral hepatitis; cholestasis; preexisting hepatic disease; or the administration of other drug(s), herbal medications, and substances known to be hepatotoxic.

This change in potential DILI definition is not anticipated to pose any risk for subjects since management of hepatic events will follow pre-established algorithms that are not impacted by the DILI definition and include dose delay and/or discontinuation as well as intervention with immunosuppressants.

## **6.7 Other Safety Considerations**

Any significant worsening noted during interim or final physical examinations, ECG, radiologic exams, or any other potential safety assessment required or not required by protocol should also be recorded as a nonserious or SAE, as appropriate, and reported accordingly.

# **7 DATA MONITORING COMMITTEE AND OTHER EXTERNAL COMMITTEES**

## **7.1 Data Monitoring Committee**

A data monitoring committee (DMC) will be established to provide oversight of safety and to provide advice to the sponsor regarding actions the committee deems necessary for the continuing protection of participants. The DMC will be charged with assessing such actions in light of an acceptable benefit-risk profile for BMS-986016. The DMC will act in an advisory capacity to BMS and will monitor participant safety and evaluate the available efficacy data for the study. The oncology therapeutic area of BMS has primary responsibility for design and conduct of the study. The DMC will meet as outlined in the DMC charter or as needed on an ad hoc basis. Information regarding DMC membership, responsibilities, and procedures are detailed in the DMC charter. The DMC will be informed should a safety signal emerge and may convene an ad hoc meeting on its own initiative. When required, adjudicated events will be submitted to the DMC and Health Authorities for review. The DMC will review all available data (safety and efficacy) at each meeting. At the conclusion of each DMC meeting, the committee will provide the Sponsor with a recommendation to continue, modify, or terminate the study protocol based upon their review. Ultimately, decisions regarding the study protocol will be made by the Sponsor in conjunction with feedback from Investigators and the DMC.

## **7.2 Blinded Independent Central Review Committee**

A BICR committee may be used in selected disease cohorts in Part C, Part D, and Part E.

## **8 STATISTICAL CONSIDERATIONS**

### **8.1 Sample Size Determination**

#### **8.1.1 *Dose Escalation (Parts A and B )***

Sample size at each dose depends on observed toxicity and cannot be precisely determined. Parts A and B will have 3 to 9 (15 in BLRM-Copula in Part B) subjects in each cohort.

In the Part B dose escalation using BLRM-Copula, the sample size at each dose depends on observed toxicity and posterior inference. Initially, approximately 3 subjects will be treated at the starting dose level (using the new BLRM-Copula design) of BMS-986016 in combination with nivolumab. Due to the potential for early discontinuation, an additional subject(s) may be enrolled to ensure approximately 3 evaluable subjects at each dose level.

Cohort tolerability assessment and subsequent dose recommendation will occur when 2 evaluable subjects within a set have completed the DLT evaluation period. If the potential DLT occurring in any third evaluable subject regarding the specific dose level does not influence the dose recommendation by BLRM-Copula, the BLRM-Copula recommended next dose level may proceed without waiting for the third subject to complete the corresponding DLT observation period, after discussion and agreement between Sponsor and Investigators. Continuous reassessment of dose recommendation by BLRM-Copula in the combination phase will be carried out at each dose level.

During dose escalation, BLRM could recommend escalating to the next dose or skipping an entire dose level altogether. In that case, a new cohort of approximately 3 subjects will be treated at the recommended new dose. BLRM could also recommend staying at the same dose level, in which case an additional increments of approximately 3 subjects will be treated at that dose. At least 6 DLT-evaluable subjects will be treated in the selected dose cohort(s) chosen for expansion. Up to 15 subjects may be treated at any dose level for further evaluation of safety and pharmacodynamic/PK parameters as required.

#### **8.1.2 *Cohort Expansion Monotherapy (Part A1)***

A sample size of 6 subjects per cohort allows for estimation of the proportion of subjects with objective response (ie, BOR of CR + PR) within a cohort such that the maximum distance between the estimated rate and either limit of the exact 2-sided 95% Clopper-Pearson confidence interval (CI) is 47.5%.

A sample size of 12 subjects per cohort allows for estimation of the proportion of subjects with objective response (ie, BOR of CR + PR) within a cohort such that the maximum distance between the estimated rate and either limit of the exact 2-sided 95% Clopper-Pearson CI is 32.2%

#### **8.1.3 *Cohort Expansion (Part C)***

The objective of this expansion in combination with nivolumab is to support further clinical testing by demonstrating adequate safety and tolerability as well as favorable benefit-risk by assessing preliminary efficacy measured by ORR and other clinically relevant efficacy measures such as

DOOR and DCR. However, the sample size is strictly based on efficacy, specifically based on the target ORR relative to historic ORR.

Disease- and prior IO therapy-restricted cohorts will be investigated in the Part C cohort expansion: NSCLC progressed on IO therapy; melanoma progressed on anti-PD-1/anti-PD-L1; RCC naive to IO therapy; NSCLC naive to IO therapy; melanoma first line; SCCHN naive to IO therapy; bladder naive to IO therapy; gastric cancer naive to IO therapy; and HCC naive to IO therapy. The NSCLC progressing on IO therapy cohort will be analyzed as a whole and as 2 separate subgroups, refractory and relapsed, as defined in [Section 3.3.1](#). All disease cohorts will be handled independently, and there will be no multiplicity adjustment.

A multistage design will be used as a guide for each expansion cohort in order to decide whether the treatment of BMS-986016 in combination with nivolumab warrants more extensive development. At first, a 2-stage design with a reasonable false positive rate (eg, < 10%) and false negative rate (eg, < 10%) will be used for decision making based on assumptions of true (target) and historic/standard-of-care response rate for each cohort. The assumed historic and target response rates may change over time and may need to be adjusted by the time of response data from this study are available. Using a 2-stage design provides an option to stop early for futility as well as a signal of preliminary antitumor activity for strong-go early on. Enrollment may continue into stage 2 while the planned number of subjects for Stage 1 are followed for efficacy evaluable tumor assessments. There will be no stopping of a disease cohort for efficacy, although early plan for the next stage of clinical development may be initiated.

The ORRs considered to be of clinical value for further expansion of selected populations, sample size, and operational characteristics of using a 2-stage design, as an example, are provided in Table 8.1.3-1, although this is not used for statistical hypothesis testing.

